**Table 9: Myocarditis Adverse Event Management Algorithm.**

Grade of Myocarditis	Management	Follow-up
Grade 2 Symptoms with mild to moderate activity or exertion	
 
• Delay I-O therapy; hospitalization with cardiac monitoring
 
• Urgent cardiology consultation for evaluation and management                             
 
◦ Troponin and BNP
 
◦ ECG ± continuous cardiac monitoring
 
◦ Echocardiogram
 
◦ Cardiac MRI
 
 
 
• Prompt initiation of 2 mg/kg/day methylprednisolone IV or equivalent
 
	
 
• If worsens, intensify treatment according to grade
 
• Upon recovery, taper steroids over at least 1 month with close monitoring of troponin and BNP as well as for new symptoms
 
• Repeat cardiac MRI for post treatment assessment and cardiology follow-up
 
• Retreatment may be considered after recovery and completion of steroid taper
 

Grade 3: Severe with symptoms at rest or with minimal activity or exertion; intervention indicated  Grade 4: Life-threatening consequences; urgent intervention indicated (e.g., continuous IV therapy or mechanical hemodynamic support)	
 
• Permanently discontinue I-O therapy
 
• Hospitalize to intensive cardiac monitoring
 
• Cardiac evaluation to include:                             
 
◦ Troponin and BNP
 
◦ ECG ± continuous cardiac monitoring
 
◦ Echocardiogram
 
◦ Cardiac MRI
 
◦ Myocardial biopsy if feasible
 
 
 
• Immediate initiation of 2 mg/kg/day methylprednisolone IV or 1 g IV bolus
 
• Consider adding a second immunosuppressive agent
 
 
Additionally, for Grade 4:
 
 
• Hospitalize/transfer to institution with expertise in intensive cardiac monitoring
 
• Consider ATG as second agent given its immediate effect
 
	
 
• If no improvement, consider additional immunosuppression
 
• Upon recovery, taper steroids over at least 1 month with close monitoring of troponin and BNP as well as for new symptoms
 
• Repeat cardiac MRI for post treatment assessment and cardiology follow-up
 

Patients on IV steroids may be switched to an equivalent dose of oral corticosteroids (e.g. prednisone) at start of tapering or earlier, once sustained clinical improvement is observed. Lower bioavailability of oral corticosteroids should be taken into account when switching to the equivalent dose of oral corticosteroids. ATG = anti-thymocyte globulin; BNP = B-type natriuretic peptide; ECG = electrocardiogram; IV = intravenous; MRI = magnetic resonance imaging

## 18.2. Ipilimumab Safety Algorithms

**Table 10: GI Adverse Event Management Algorithm.** Rule out non-inflammatory causes. If non-inflammatory cause is identified, treat accordingly and continue ipilimumab. Opiates/narcotics may mask symptoms of perforation. Infliximab should not be used in cases of perforation or sepsis.

Grade of Diarrhea/Colitis	Management	Follow-up
Grade 1 Diarrhea:< 4 stools/day over baseline; Colitis: asymptomatic	
 
Continue ipilimumab
 
Symptomatic treatment
 
	
 
Close monitoring for worsening symptoms.
 
Educate patient to report worsening immediately
 

Grade 2 Diarrhea: 4-6 stools per day over baseline; IV fluids indicated <24 hrs; not interfering with ADL Colitis: abdominal pain; blood in stool	
 
Withhold/delay ipilimumab
 
Symptomatic treatment
 
	
Symptoms improve/resolve (grade 0/1):
 
 
Resume ipilimumab
 
 
Symptoms persists > 5-7 days, worsen, or recur:
 
 
Moderate to high dose steroids PO (e.g., prednisone 0.5-1.0 mg/kg/day)
 
Continue to hold/delay ipilimumab until grade 1
 
When symptoms are grade 1 or less, slowly taper steroids over at least 1 month and resume ipilimumab
 
 
Symptoms worsen:
 
 
Treat as grade 3/4
 

Grade 3-4 Diarrhea (G3*): ≥7 stools per day over baseline; incontinence; IV fluids ≥24 hrs; interfering with ADL Colitis (G3*): fever, ileus, peritoneal signs	
 
Permanently discontinue ipilimumab
 
High dose IV steroids (e.g., 1-2 mg/kg/day methylprednisolone)
 
Consider endoscopy
 
	
Symptoms improve:
 
 
Continue steroids (same dose) until grade 1
 
Then taper over at least 1 month
 
 
Symptoms persist 3-5 days, or recur after improvement:
 
 
1 dose* infliximab 5 mg/kg (if no contraindication)
 

\*G4: life-threatening, perforation

\*Some patients have required a second dose of infliximab

Patients on IV steroids may be switched to an equivalent dose of oral corticosteroids (e.g. prednisone) at start of tapering or earlier, once sustained clinical improvement is observed. Lower bioavailability of oral corticosteroids should be taken into account when switching to the equivalent dose of oral corticosteroids.

**Table 11: Hepatic Adverse Event Management Algorithm.** Rule out non-inflammatory causes. If non-inflammatory cause, treat accordingly and continue I-O therapy. Consider imaging for obstruction.

Grade of Liver Test Elevation	Management	Follow-up
Grade 1 AST or ALT $\leq$ 2.5 x ULN Or Total bilirubin $\leq$ 1.5 x ULN	
 
Continue ipilimumab
 
	
 
Continue LFT monitoring prior to each dose
 

Grade 2 AST or ALT $>$ 2.5 to $\leq$ 5 x ULN or Total bilirubin $>$ 1.5 to $\leq$ 3 x ULN	
 
Increase frequency of monitoring (q3d)
 
Withhold/delay ipilimumab while investigating alternative etiology
 
	Return to baseline: 
 
Resume q3w monitoring
 
Resume ipilimumab
 
 Elevations persist > 5-7 days or worsen, and no alternative etiologies are identified: 
 
Consider moderate to high dose steroids PO (e.g., 0.5-1 mg/kg/day prednisone or equivalent)
 

Grade 3-4 AST or ALT $>$ 5 x ULN or Total bilirubin $>$ 3 x ULN	
 
Discontinue ipilimumab*
 
Increase frequency of monitoring (q1-3d)
 
High dose IV steroids (e.g., 1-2 mg/kg/day methylprednisolone**)
 
	AST/ALT/Tbili returns to Grade 2: 
 
Taper steroids over at least 1 month
 
 Labs do not decrease over 3-5 days, worsen or rebound: 
 
Add mycophenolate mofetil 1 g BID
 
If no response within 3-5 days, consider other immunosuppressants per local guidelines
 

\*Ipilimumab may be held/delayed rather than discontinued if AST/ALT  $\leq$  8 X ULN and Tbili  $<$  5 X ULN. Resume ipilimumab when AST/ALT/Tbili return to grade 2 and meet protocol specific retreatment criteria.

\*\*The recommended starting dose for grade 4 hepatitis is 2 mg/kg/day methylprednisolone IV.

Patients on IV steroids may be switched to an equivalent dose of oral corticosteroids (e.g. prednisone) at start of tapering or earlier, once sustained clinical improvement is observed. Lower bioavailability of oral corticosteroids should be taken into account when switching to the equivalent dose of oral corticosteroids.

**Table 12: Endocrinopathy Adverse Event Management Algorithm.** Rule out non-inflammatory causes. If non-inflammatory cause, treat accordingly and continue ipilimumab.

Asymptomatic TSH Elevation	
 
Continue ipilimumab
 
If TSH < 0.5 x LLN, or TSH > 2 x ULN, or consistently out of range in 2 subsequent measurements: include fT4 at subsequent cycles as clinically indicated; consider endocrinology consult
 
	
Symptomatic endocrinopathy	
 
Evaluate endocrine function
 
Consider pituitary scan
 
 
Symptomatic with abnormal lab/pituitary scan:
 
 
Withhold/delay ipilimumab
 
High dose IV steroids (e.g., 1-2 mg/kg/day methylprednisolone)
 
Initiate appropriate hormone therapy
 
 
No abnormal lab/pituitary scan but symptoms persist:
 
 
Repeat labs in 1-3 weeks / MRI in 1 month
 
	
Symptoms resolve (with or without hormone replacement):
 
 
Taper steroids over at least 1 month
 
Resume ipilimumab
 
Patients with adrenal insufficiency may need to continue steroids with mineralocorticoid component
 

Suspicion of adrenal crisis (e.g., severe dehydration, hypotension, shock out of proportion to current illness)	
 
Rule out sepsis
 
Stress dose of IV steroids with mineralocorticoid activity
 
IV fluids
 
Consult endocrinologist
 
If adrenal crisis ruled out, then treat as above for symptomatic endocrinopathy
 
	

Patients on IV steroids may be switched to an equivalent dose of oral corticosteroids (e.g. prednisone) at start of tapering or earlier, once sustained clinical improvement is observed. Lower bioavailability of oral corticosteroids should be taken into account when switching to the equivalent dose of oral corticosteroids.

**Table 13: Skin Adverse Event Management Algorithm.** Rule out non-inflammatory causes. If non-inflammatory cause, treat accordingly and continue ipilimumab.

Grade of Rash	Management	Follow-up
Grade 1-2	
 
Symptomatic therapy (e.g., antihistamines, topical steroids)
 
Continue ipilimumab
 
	
Symptoms resolve: continue ipilimumab
 
If persists > 1-2 weeks or recurs:
 
 
Continue ipilimumab
 
Moderate to high dose steroids PO (e.g., 0.5-1.0 mg/kg/day Iprednisone)
 
Once controlled, taper steroids over at least 1 month
 

Grade 3-4	
 
Hold/delay ipilimumab (regardless of relationship)
 
Take photos of rash
 
Consider skin biopsy
 
Dermatology consult
 
High dose IV steroids (e.g., 1-2 mg/kg/day methylprednisolone)
 
	
Symptoms resolve / return to Grade 1:
 
 
Taper steroids over at least 1 month
 
Resume ipilimumab
 
Discontinue if grade 4 toxicity considered related
 

Patients on IV steroids may be switched to an equivalent dose of oral corticosteroids (e.g. prednisone) at start of tapering or earlier, once sustained clinical improvement is observed. Lower bioavailability of oral corticosteroids should be taken into account when switching to the equivalent dose of oral corticosteroids.

**Table 14: Neurological Adverse Event Management Algorithm.** Rule out non-inflammatory causes. If non-inflammatory cause, treat accordingly and continue ipilimumab. Discontinue ipilimumab for any grade 3-4 motor neuropathy, regardless of relationship.

Severity of Neurological Toxicity	Management	Follow-up
Grade 1	
 
Continue ipilimumab
 
	
 
Continue to monitor the patient. If symptoms worsen, treat as below
 

Grade 2	
 
Hold/delay ipilimumab
 
Treat symptoms per local guidelines
 
	
 
Resume ipilimumab when resolved/grade 1. If symptoms worsen, treat as below.
 

Grade 3-4 sensory	
 
Discontinue ipilimumab if considered related
 
Obtain neuro consult
 
Treat symptoms per local guidelines
 
High dose IV steroids (e.g., 1-2 mg/kg/day methylprednisolone)
 
	
Symptoms resolve / return to Grade 2:
 
 
Taper steroids over at least 1 month
 

Grade 3-4 motor	
 
Discontinue ipilimumab regardless of relationship
 
Obtain neuro consult
 
Treat symptoms per local guidelines
 
High dose IV steroids (e.g., 1-2 mg/kg/day methylprednisolone)
 
	
Symptoms resolve / return to Grade 2:
 
 
Taper steroids over at least 1 month
 
 
Symptoms do not resolve or progress; atypical presentation:
 
 
Consider IVIg or other immunosuppressive therapies per local guidelines
 

Patients on IV steroids may be switched to an equivalent dose of oral corticosteroids (e.g. prednisone) at start of tapering or earlier, once sustained clinical improvement is observed. Lower bioavailability of oral corticosteroids should be taken into account when switching to the equivalent dose of oral corticosteroids.

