### **9.1.2. Dose Modification**

#### **9.1.2.1. Non-hematologic:**

Not applicable, only one dose of the study drug is given so there will be no intra-patient dose reduction. Similarly, the proposed doses of 3 mg/kg for nivolumab and 1 mg/kg for ipilimumab are recommended by the FDA.

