Grade 2-3 Mild to moderate new symptoms	
 
Delay I-O therapy per protocol
 
Pulmonary and ID consults
 
Monitor symptoms daily, consider hospitalization
 
1.0 mg/kg/day methylprednisolone IV or oral equivalent
 
Consider bronchoscopy, lung biopsy
 
	
 
Re-image every 1-3 days
 
 
If improves:
 
 
When symptoms return to near baseline, taper steroids over at least 1 month and then resume I-O therapy per protocol and consider prophylactic antibiotics
 
 
If not improving after 2 weeks or worsening:
 
 
Treat as Grade 3-4
 

Grade 4 Severe new symptoms; New/worsening hypoxia; Life-threatening	
 
Discontinue I-O therapy per protocol
 
Hospitalize
 
Pulmonary and ID consults
 
2-4 mg/kg/day methylprednisolone IV or IV equivalent
 
Add prophylactic antibiotics for opportunistic infections
 
Consider bronchoscopy, lung biopsy
 
	
If improves to baseline:
 
 
Taper steroids over at least 6 weeks
 
 
If not improving after 48 hours or worsening:
 
 
Add additional immunosuppression
 

Patients on IV steroids may be switched to an equivalent dose of oral corticosteroids (e.g. prednisone) at start of tapering or earlier, once sustained clinical improvement is observed. Lower bioavailability of oral corticosteroids should be taken into account when switching to the equivalent dose of oral corticosteroids.

**Table 5: Hepatic Adverse Event Management Algorithm.** Rule out non-inflammatory causes. If non-inflammatory cause, treat accordingly and continue I-O therapy. Consider imaging for obstruction.

Grade of Liver Test Elevation	Management	Follow-up
Grade 1 AST or ALT > ULN to 3.0 x ULN and/or T. bili > ULN to 1.5 x ULN	
 
Continue I-O therapy per protocol
 
	
 
Continue LFT monitoring per protocol
 
 
If worsens:
 
 
Treat as Grade 2 or 3-4
 

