Grade 2 AST or ALT > 3.0 to ≤ 5 x ULN and/or T. bili > 1.5 to ≤ 3 x ULN	
 
Delay I-O therapy per protocol
 
Increase frequency of monitoring to every 3 days
 
	
If returns to baseline:
 
 
Resume routine monitoring, resume I-O therapy per protocol
 
 
If elevation persists > 5-7 days or worsens:
 
 
0.5-1 mg/kg/day methylprednisolone or oral equivalent and when LFT returns to grade 1 or baseline, taper steroids over at least 1 month, consider prophylactic antibiotics for opportunistic infections, and resume I-O therapy per protocol
 

Grade 3-4 AST or ALT > 5 x ULT or T. bili > 3 x ULN	
 
Discontinue I-O therapy per protocol*
 
Increase frequency of monitoring to every 1-2 days
 
1.0 to 2.0 mg/kg/day methylprednisolone IV or IV equivalent*
 
Add prophylactic antibiotics for opportunistic infections
 
Consult gastroenterologist
 
	
If returns to Grade 2:
 
 
Taper steroids over at least 1 month
 
 
If does not improve in >3-5 days, worsens or rebounds:
 
 
Add mycophenolate mofetil 1 g BID
 
If no response within an additional 3-5 days, consider other immunosuppressants per local guidelines
 

Patients on IV steroids may be switched to an equivalent dose of oral corticosteroids (e.g. prednisone) at start of tapering or earlier, once sustained clinical improvement is observed. Lower bioavailability of oral corticosteroids should be taken into account when switching to the equivalent dose of oral corticosteroids.

\*The recommended starting dose for grade 4 hepatitis is 2 mg/kg/day methylprednisolone IV.

**Table 6: Endocrinopathy Adverse Event Management Algorithm.** Rule out non-inflammatory causes. If non-inflammatory cause, treat accordingly and continue I-O therapy. Consider visual field testing, endocrinology consultation, and imaging.

Asymptomatic TSH Elevation	
 
Continue I-O therapy per protocol
 
If TSH < 0.5 x LLN, or TSH > 2 x ULN, or consistently out of range in 2 subsequent measurements: include fT4 at subsequent cycles as clinically indicated; consider endocrinology consult
 
	

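### Tables 5 and 11 grade AST/ALT between 2.5 and 3.0 x ULN differently although every patient receives both drugs, and Table 11's Grade 1 follow-up presupposes repeat dosing

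*Combined protocol and SAP*

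**What the plan says.** Section 9.1 gives every eligible participant one infusion of each drug before surgery. Section 9.1.2.1 states that "only one dose of the study drug is given so there will be no intra-patient dose reduction". For managing adverse events, Section 13.1 refers to Section 18.1 for nivolumab and Section 18.2 for ipilimumab. It does not say which applies when a patient has received both.

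In Table 5 (Section 18.1), hepatic Grade 1 is "AST or ALT > ULN to 3.0 x ULN and/or T. bili > ULN to 1.5 x ULN", followed by liver tests on the protocol's ordinary schedule. Grade 2 starts at "AST or ALT > 3.0 to ≤ 5 x ULN", with the instruction "Increase frequency of monitoring to every 3 days".

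In Table 11 (Section 18.2), Grade 1 ends for the enzymes at a lower multiple (the cell reads in part "2.5 x ULN Or Total bilirubin"), and Grade 2 runs from above 2.5 to 5 x ULN. The Grade 1 follow-up is "Continue LFT monitoring prior to each dose". The Grade 2 instruction is "Increase frequency of monitoring (q3d"), that is, every 3 days.

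**The concern.** The two tables apply to the same people. If they assign one laboratory value to different grades, the investigator has two written instructions for one patient and no rule for choosing between them. After a single dose, the wording on continuing, holding or resuming treatment has no effect. The monitoring interval does, because it concerns toxicity that appears after the infusion, and adverse events are collected until 100 days after surgery (Section 13.1). At stake is how soon a mild rise in liver enzymes is rechecked. A second, smaller matter is a follow-up line that depends on later doses the protocol does not contain.

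**Working it through.** The plan has no figure to reproduce here. The check is a side-by-side reading of the two tables, followed by simple arithmetic on the visit schedule.

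**Step 1. The tables compared**

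| Item | Table 5 (nivolumab) | Table 11 (ipilimumab) | Result |
|---|---|---|---|
| AST/ALT, Grade 1 upper limit | 3.0 x ULN | 2.5 x ULN | conflict |
| AST/ALT, Grade 2 | >3.0 to 5 x ULN | >2.5 to 5 x ULN | conflict at the lower end |
| AST/ALT, Grade 3-4 | >5 x ULN | >5 x ULN | agree |
| Bilirubin limits | 1.5 and 3 x ULN | 1.5 and 3 x ULN | agree |
| Grade 1 follow-up | scheduled visits | before each dose | conflict; the second cannot be carried out |
| Grade 2 monitoring | every 3 days | every 3 days | agree |
| Grade 2, back to baseline | routine | every 3 weeks | differ |
| Grade 2, persistent | steroids instructed | steroids to be considered if no other cause is found | differ in strength |
| Grade 3-4 monitoring | every 1-2 days | every 1-3 days | differ slightly |

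**Step 2. The disputed band.** The grades differ only for AST or ALT above 2.5 and up to 3.0 x ULN. Take 2.8 x ULN as an example. Since 2.8 < 3.0, Table 5 gives Grade 1 and the next scheduled test. Since 2.8 > 2.5, Table 11 gives Grade 2 and a test within 3 days.

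**Step 3. What the difference means in time.** Assume that the CMP includes AST and ALT; Section 12.7.4 does not list its components. Table 1 and Sections 12.2 to 12.4 schedule a CMP on Day 1, at Week 3 (±1 week), Week 7 (±1 week) and Week 13 (±2 weeks), and none at the Week 4 radiosurgery visit. For a value found at Week 3, the next check under Table 5 is:

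- nominal: 7 − 3 = 4 weeks
- shortest: (7 − 1) − (3 + 1) = 2 weeks
- longest: (7 + 1) − (3 − 1) = 6 weeks

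Under Table 11 it is 3 days. For a value found on Day 1, the nominal interval under Table 5 is 3 − 1 = 2 weeks. For one found at Week 7 it is 13 − 7 = 6 weeks, unless a standard-of-care visit falls in between.

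**Step 4. The dose-linked line.** Protocol doses of ipilimumab: 1. Doses remaining after the infusion: 1 − 1 = 0. Testing before each dose therefore produces no test after treatment. The other Table 11 intervals (every 3 days, every 1-3 days, every 3 weeks) are calendar intervals and can be followed without further dosing, although the 3-week interval reads as carried over from a repeat-dose course.

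**The case against.** The case for leaving this alone has several parts.

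- **Grading and attribution are set elsewhere.** Section 13.1 grades adverse events by CTCAE version 5 and requires attribution to a named drug, which could be read as the route to one table or the other. This does not settle the matter. When both drugs are given in the same visit window, a rise in liver enzymes can be attributed to both. The documents also do not reproduce the CTCAE limits, so they do not show which table matches version 5.
- **Most of the content agrees.** This stands, and it confines the grading conflict to one enzyme band.
- **The steroid wording is not a contradiction.** This also stands. The trigger and the numerical dose range are the same, and Table 5 itself opens by asking that non-inflammatory causes be excluded. An investigator who follows Table 5 does not breach Table 11.
- **Patients are still monitored.** This stands too. Scheduled CMPs continue whatever the Grade 1 line says, and an investigator may order more.
- **Repeat-dose wording runs through nearly all the appendix tables,** Table 5 included. That is correct, and it is a reason to correct it generally.

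A reader might also infer that the conflict leaves liver toxicity unmanaged in the days before craniotomy. The schedule does not support that: the first CMP planned after the infusion is on Day 1, just before resection, and the intervals in Step 3 all start on Day 1 or later.

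**Conclusion.** The point holds in a narrow form. For AST or ALT above 2.5 and up to 3.0 x ULN, the protocol gives two grades and two recheck intervals for the same patient, with no rule of precedence. From Week 3 that is 3 days against nominally 4 weeks (2 to 6 with the visit windows), provided the CMP contains liver tests. Separately, Table 11's Grade 1 follow-up cannot be carried out in a single-dose study.

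A reader might go further and conclude that ipilimumab liver monitoring as a whole depends on doses never given. The documents do not support this, since only the Grade 1 line is tied to dosing. Nor do they show that the two algorithms contradict each other at every grade; outside the disputed band and that line, the differences are of emphasis or small.

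The documents do not say how many of the up to 20 patients might fall in the band. Section 11.1 sets no AST or ALT limit, so a patient could enter the study in it. Adverse events are tabulated by CTCAE version 5 (Section 15.5.1.3), and neither hepatic table bears on the surgical-delay definition or the Ki67 analysis. The consequence is for patient management, not for the primary analyses.

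**What to change.** Reconcile Tables 5 and 11 with each other, with CTCAE version 5 as named in Section 13.1, and with the single-dose design, so that one set of AST/ALT limits and one follow-up schedule applies to patients who received both drugs. In the same revision, align the wording on steroids for persistent Grade 2 and on Grade 3-4 monitoring, and replace the dose-linked Grade 1 line with an instruction that can be carried out after one infusion. Stating in Section 12.7.4 whether the CMP includes AST, ALT and bilirubin would remove the assumption made above. Which limits and which schedule apply is for the clinical team to decide. The cost is a change to appendix wording in the next amendment, with no change to the sample size, the endpoints or the analyses.
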